For a full list of study procedures, including the timing of each procedure, please refer to [Section 7](#) and the Schedule of Assessments ([Table 5](#) and [Table 6](#)).

Statistical Considerations:

Phase 1b:

Sample size considerations:

For phase 1b, 6 to 9 evaluable subjects will be required to assess the DLT profile of talimogene laherparepvec in combination with pembrolizumab. Additional subjects, to a total of 20, will be enrolled in the phase 1b portion of the trial to address the secondary objective exploring the relationship between [REDACTED] and response to treatment.

Planned method of analyses:

The efficacy and safety data will be summarized separately for phase 1b and phase 3.

The phase 1b safety analysis is planned when there are 6 to 9 DLT evaluable subjects.

For phase 1b, besides a summary of the incidence of DLTs, descriptive statistics will be provided for demographics, safety, efficacy, and [REDACTED] as appropriate.

Treatment effects in efficacy endpoints in phase 3 will be according to the treatment group as randomized. Frequency and percent of subjects for binary and categorical efficacy endpoints will be summarized by treatment arm. Proportions and 95% confidence interval using a normal approximation will also be provided. Treatment comparisons will be based on Cochran-Mantel-Haenszel test. Exact tests will be used for subgroup analyses when cell sizes are too small. Analysis of time-to-event endpoints will be based on K-M estimation. Hazard ratios (HRs) will be estimated using Cox proportional hazards (PH) model.

Phase 3:

Sample size considerations:

There are 2 primary endpoints, PFS and OS, in phase 3. The hypothesized reduction of 1/3 hazard for PFS (talimogene laherparepvec and pembrolizumab / pembrolizumab and placebo) is equivalent to an HR of 0.67 and the hypothesized HR for OS is 0.70. Initial allocation of significance level, overall 2-sided 0.05, is 2-sided 0.005 for PFS and 2-sided 0.045 for OS. The event goal for PFS to achieve 90% power at 2-sided 0.005 is 407. The event goal for OS adjusted for 4 group sequential analyses to achieve 90% power at a 2-sided 0.045 is 346. The sample size is 660 subjects (ie, 330 per arm) based on an estimate of 346 death events occurring within 5 years (60 months).

Planned method of analyses:

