The primary analysis of PFS will be based on tumor assessments per the blinded independent central review using modified RECIST 1.1. For analyses of the 2 primary endpoints PFS and OS, a stratified log-rank test will be used as the primary method for testing the null hypothesis of no treatment difference. The stratification factors will include randomization factors per IVRS and PD-L1 status at baseline (positive vs not positive). Hazard ratios will be estimated using the Cox proportional hazards (PH) model stratified by randomization factors per IVRS and the baseline PD-L1 status (positive vs not positive). Multiple statistical testing for the dual primary endpoints

Approved

and the 3 secondary endpoints of iCRR, iPFS, and OS in subjects excluding disease stage IVM1c will follow a graphic-based, multiple group sequential hypotheses testing procedure (Maurer and Bretz, 2013) to ensure a strong control of an overall Type I error of 0.05 (see Section 10.5). The information fraction will be based on the number of events included in the respective analysis for all time to event endpoints, and it will be based on the number of subjects with potential follow-up of at least 36 weeks for iCRR. The nominal alpha will be transitioned to test hypotheses for the 3 secondary endpoints if either the primary endpoint of PFS or OS is statistically significant.

Two interim safety analyses are planned to evaluate the safety of talimogene laherparepvec in combination with pembrolizumab in the target population for the phase 3. Planned safety monitoring will occur when approximately 20 and 100 total subjects, respectively, have had the opportunity to be on treatment for at least 6 weeks from the initial dosing of study treatment in phase 3 and have received at least 1 dose of study therapy.

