3.1.2 Phase 3 Study Design

The phase 3 study is a double-blind, placebo-controlled, multicenter, randomized trial to evaluate the efficacy, as assessed by PFS and OS of talimogene laherparepvec with pembrolizumab versus placebo with pembrolizumab in subjects with unresectable, stage IIIB to IVM1c melanoma. Approximately 660 subjects will be randomized 1:1 to receive the following:

- Arm 1: talimogene laherparepvec plus pembrolizumab
- Arm 2: placebo plus pembrolizumab

Randomization will be stratified by stage of disease: less advanced stages (IIIB, IIIC, and IVM1a) versus more advanced stages (IVM1b and IVM1c) and by prior serine/threonine protein kinase B-Raf BRAF inhibitor therapy: no prior BRAF inhibitor versus prior BRAF inhibitor with or without MEK inhibitor.

Approved

Talimogene laherparepvec/placebo and pembrolizumab treatment will be initiated simultaneously. When talimogene laherparepvec/placebo and pembrolizumab are administered on the same day, talimogene laherparepvec/placebo should be administered first, if possible.

Talimogene laherparepvec/placebo will be administered as an intralesional injection up to 4 mL of 10^6 PFU/mL at day 1 of week 0 followed by up to 4 mL of 10^8 PFU/mL at day 1 of week 3 (ie, 21 days later [+3 days]), and every 2 weeks (\pm 3 days) until the fifth injection of talimogene laherparepvec/placebo (week 9) and then be dosed synchronously with pembrolizumab thereafter every 3 weeks (\pm 3 days). Talimogene laherparepvec/placebo should be administered until disappearance of injectable lesions, iCR, documented confirmed progressive disease (iPD) per modified irRC-RECIST ([Appendix F](#)), intolerance of study treatment, 24 months from the date of the first dose of talimogene laherparepvec/placebo, or end of study, whichever occurs first. Due to the mechanism of action, subjects may experience growth in existing tumors or the appearance of new tumors prior to maximal clinical benefit of talimogene laherparepvec. Therefore, dosing should continue provided that the subject has no evidence of confirmed iPD per modified irRC-RECIST ([Appendix F](#)) and is able to tolerate the treatment.

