10.2 Sample Size Considerations

10.2.1 Sample Size Considerations for Phase 1b

Six to nine DLT-evaluable subjects will be required to assess the DLT profile of talimogene laherparepvec in combination with pembrolizumab for phase 1b. The sample size of approximately 6 to 9 subjects is determined empirically and is consistent with those used in 6+3 phase 1 designs to evaluate the safety of a single dose of each agent assuming a true incidence rate of DLT is 11 to 33%. Additional subjects, up to a total of 20, will be enrolled in the phase 1b portion of the trial to address the secondary objective exploring the relationship between [REDACTED] and response to treatment.

[figure not shown]

10.2.2 Sample Size Considerations for Phase 3

There are 2 primary endpoints for phase 3, PFS and OS. A 1/3 reduction in hazard ratio (talimogene laherparepvec with pembrolizumab / placebo with pembrolizumab) for PFS (HR = 0.67), and a hazard ratio of 0.70 for OS are hypothesized in the Full Analysis Set. Assuming events follow piece-wise exponential distributions (Figure 1 and Figure 2), the hypothesized HRs will translate into a relative increase of 167% in median PFS time and 44% in median OS time. The absolute increase in median PFS will be 9.4 months (5.6 to 15.0 months) in the talimogene laherparepvec and placebo arm and 12.4 months (28 to 40.4 months) in median OS.

[figure not shown]
Approved

Figure 1. Progression-free Survival

Median PFS (pembrolizumab), 5.6 months; $p(t)$ = event rate at month t ; $p(1.5) = 0.95$; $p(3) = 0.6$; $p(6) = 0.49$; $p(12) = 0.39$; $p(18) = 0.32$; $p(24) = 0.30$; constant hazard in each interval between 2 consecutive pieces; a constant hazard ratio across all pieces.

Figure 2. Overall Survival

Median OS (pembrolizumab) = 28 months; $p(t)$ = event rate at month t ; $p(48) = 0.31$ and $p(60) = 0.27$; constant hazard in each interval between 2 consecutive pieces; a constant hazard ratio across all pieces.

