1. The initial alpha allocation for testing the hypothesis of PFS (H_2) is 0.5% and 4.5% for OS (H_1). There will not be a nominal alpha passed back to H_2 after rejecting H_1 or other hypotheses at any analysis.
2. An interim OS analysis will be performed at Analysis #1 with all death events, regardless if H_2 is rejected. In the event when Analysis #2 occurs prior to Analysis #1, then it will include an interim analysis to test H_2 for PFS (using all PFS events) and, if H_2 is not rejected, it will be tested again at the planned time for Analysis #1. However, if the projected time for achieving 407 PFS events is within 4 months from the projected 282 OS events time, then Analysis #2 will be combined with Analysis #1 and be performed at Analysis #1 using all death events with PFS times censored after the 407th PFS event.
3. At each of the 5 planned analysis times, it will be considered an interim analysis of iCRR and iPFS, rather than the primary analysis, if the maximum information has not been reached for the respective endpoint at that time. For example, if H_3 is tested in an analysis that includes fewer than 256 iPFS events, then it will be an interim analysis of iPFS that includes all observed events; otherwise, it will be the primary analysis with all iPFS times censored after the date of the 256th event. If all randomized subjects do not have at least 36 weeks follow-up in an analysis, then it will be an interim analysis for iCRR only including those subjects with at least 36 weeks follow-up; otherwise, it will be the primary analysis and include all randomized subjects. With the exception of PFS, the hypothesis for an endpoint may be re-tested after its primary analysis using its primary analysis data if alpha is subsequently propagated to it from the rejection of another hypothesis.
4. Assuming Analysis #1 is before Analysis #2, and at Analysis #1 the null hypothesis of PFS (H_2) is rejected, the hypotheses H_3 and H_4 will be tested. H_1 will be tested at Analysis #1 regardless of whether H_2 is rejected. The iPFS (H_3) and iCRR (H_4) can be tested if H_2 is not rejected but H_1 is significant. Likewise, OS subgroup (H_5) can be tested at Analysis #1 if any of the following set of hypotheses are rejected: (1) H_2 and H_3 ; (2) H_2 and H_4 ; (3) H_1 and H_3 ; or (4) H_1 and H_4 .

Approved

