Appendix B. Nominal Significance Levels for Maurer-Bretz Multiple Testing

Multiple testing will be conducted on primary endpoints (OS and PFS) and three secondary endpoints (iPFS, iCRR and OS subgroup excluding disease stage IVM1c) at 5 planned analyses for the study: PFS PA or OS IA1 (407 PFS events), OS IA2 (282 deaths), **OS IA3 (315 deaths)**, OS PA (346 deaths), and OS in subgroup (208 deaths). At the time of 1st interim analysis, the nominal significant level depends on the information fractions observed where the spending function mimics the O'Brien-Fleming (OBF) boundaries:

$$\alpha(\gamma, y) = 2 \left(1 - \Phi \left(\Phi^{-1}(1 - \gamma/2) / \sqrt{y} \right) \right)$$

Where

γ = 1-sided overall significance level

y = information fraction at the analysis time point

Φ = cumulative normal.

Based on the progress of the study, the PFS PA will be the 1st analysis and thus, the information fraction is 100% for this endpoint. At the time of PFS PA, it is likely that the information for hypotheses testing on OS, iPFS and OS subgroup will be partial and iCRR will be full information because all enrolled subjects will have been followed for more than 6 months.

Figure 2 to Figure 5 below illustrate the Maurer-Bretz successive sequential testing procedure for (1) the initial test of primary endpoints; (2) testing secondary endpoints (iPFS and iCRR); (3) testing secondary endpoint (OS subgroup); (4) possible re-test of one of the primary endpoints, OS, when rejection of both PFS and OS subgroup endpoints occur (note PFS cannot be re-tested at PFS PA or any subsequent analyses).

Table 5 provides the nominal significance levels for all possible scenarios at the PFS PA as illustrated in Figure 2 to Figure 5 under a set of information fractions assumed as: **252/346** for OS, **100%** for iPFS and iCRR, and 168/208 for OS subgroup. Note because nominal significance levels are very small, to avoid rounding error, the observed number of events out of the target number of events should be used to calculate information fractions for OS, iPFS, and OS subgroup. Upon the PFS PA snapshot (lock), this table will be re-calculated for all possible significance levels for these endpoints by replacing the observed number of events for the 3 endpoints (OS, iPFS, and OS subgroup).

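### No alpha can return to PFS, so 0.045 goes unused once the other four tested hypotheses are rejected: a free gain in PFS power forgone, not an error

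*Protocol*

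**What the plan says.** The Synopsis (Statistical Considerations, Phase 3) sets the split: "Initial allocation of significance level, overall 2-sided 0.05, is 2-sided 0.005 for PFS and 2-sided 0.045 for OS". It sizes PFS at that level: "The event goal for PFS to achieve 90% power at 2-sided 0.005 is 407".

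The Synopsis sentence on transferring alpha ("The nominal alpha will be transitioned to test hypotheses for the 3 secondary endpoints if either the primary endpoint of PFS or OS" succeeds) covers only the step from the primaries to the three tested secondaries. The operative rule is in Protocol 10.4.1.4, repeated in SAP 8.1.4. Item 1: "There will not be a nominal alpha passed back to" H2 (PFS) after rejecting H1 (OS) or any other hypothesis, at any analysis. Item 3: "With the exception of PFS, the hypothesis for an endpoint may be re-tested after its primary analysis using its primary analysis data" if alpha later reaches it. SAP Appendix B repeats the bar: "note PFS cannot be re-tested at PFS PA or any subsequent analyses".

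Protocol 10.5.1 and SAP 10.5.1.1 otherwise allow repeated re-testing at whatever level other rejections release. OS can rise to the full 0.05 (Protocol Table 12 footnote; re-test rows of SAP Table 5), and items 3 and 8 let iPFS and iCRR be re-tested on frozen data. No reason is given for excluding PFS.

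**The concern.** PFS is one of two primary endpoints, yet it is the only hypothesis barred from re-testing. When OS, iPFS and iCRR are rejected and PFS is not, SAP Table 5 puts weight 9/10, or 0.045, on the OS subgroup. If the subgroup is rejected too, PFS is the only hypothesis left and may not receive that alpha.

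What is at stake is a formal PFS claim. For example, an observed PFS hazard ratio of 0.78 on 407 events (p about 0.012) could not be claimed, even with OS and all three tested secondaries significant.

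**Working it through.** **1. The plan's own figure.** Inputs: 407 events, two-sided 0.005, 90% power (Synopsis; Protocol 10.2.2), 1:1 allocation, and a one-third hazard reduction, so HR = 2/3 (printed as 0.67). Schoenfeld's formula:

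D = 4(z₀.₉₉₇₅ + z₀.₉₀)² / (ln HR)² = 4(2.807 + 1.282)² / (ln 2/3)² = 406.7, so 407.

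This matches the plan. The stated 90% therefore relies on no recycled alpha.

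**2. Critical hazard ratios at 407 events**, exp(−2z/√407):
- at 0.005: exp(−2 × 2.807/20.17) = 0.757 (Protocol Table 12 prints 0.76)
- at 0.05: exp(−2 × 1.960/20.17) = 0.823

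The example: z = −ln(0.78) × 20.17/2 = 2.51, p = 0.012, which lies between the two levels.

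**3. The graph.** The figures are not shown, so the edges were inferred from SAP Table 5:
- OS to iPFS 0.8, iCRR 0.2 (0.9 × 0.8 = 0.72; 0.9 × 0.2 = 9/50)
- PFS to iPFS 0.9, iCRR 0.1 (0.1 × 0.9 = 9/100; 0.1 × 0.1 = 1/100)
- iPFS to iCRR 0.9, OS subgroup 0.1 (0.01 + 0.09 × 0.9 = 91/1000; 0.09 × 0.1 = 9/1000)
- iCRR to iPFS 0.9, OS subgroup 0.1 (0.09 + 0.01 × 0.9 = 99/1000)
- OS subgroup to OS 1 (0.9 + 0.009 = 0.909)

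Each bracketed value agrees with Table 5. With all but PFS rejected, the rebuilt graph leaves PFS at 0.1 × 0.05 = 0.005, and 0.05 − 0.005 = 0.045 goes unused.

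**4. Upper bound on the gain.** If the other four were always rejected, PFS power would be Φ(4.090 − 1.960) = 98.3%, against Φ(4.090 − 2.807) = 90.0% now: at most 8.3 points.

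**5. Simulated gain.** The graph was run with and without a vanishing edge from OS subgroup to PFS. It used one-time analyses, as Protocol Table 10 does. Expected z-values from the design effects: OS 3.32, PFS 4.09, iPFS 4.09, iCRR 5.47, OS subgroup 3.68. Assumed correlations: 0.2 to 0.5 in general, 0.7 for PFS with iPFS, √(208/346) for OS with its subgroup. At correlation 0.5 the plan's powers came out at 91/90/95/97/90%, against 91/90/94/97/90% in Table 10 (OS, PFS, iPFS, iCRR, OS subgroup). The other four were all rejected in about 88% of runs.

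| PFS HR | Other effects | PFS power, plan | With return |
|---|---|---|---|
| 2/3 | design values | 90% | about 95-97% |
| 0.75 | all shrink in proportion | about 54-55% | 65-67% |
| 0.75 | only iPFS shrinks with PFS | about 54-55% | 73-77% |
| 0.75 | all stay at design values | about 54-55% | 79% |
| 0.80 | all shrink in proportion | about 29% | 37-39% |
| 0.80 | only iPFS shrinks with PFS | about 29% | 49-55% |
| 0.80 | all stay at design values | about 29% | 59-61% |

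The 97% end of the first row comes from independent statistics. The middle rows span two readings of proportional shrinkage for iPFS (log hazard ratio or hazard ratio).

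**6. Cost to the other hypotheses and to error control.** Decisions on OS, iPFS, iCRR and the OS subgroup were identical with and without the edge. Simulated familywise error under the global null was 5.0% both ways. With PFS null and the other four effects very large it was 0.5% under the plan and 4.8% with the return, within the 0.05 target.

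**The case against.** The strongest reply is that this is a deliberate rule, stated in both documents without contradiction, and conservative. That stands: no result would be invalid or ambiguous because of it.

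A reader might infer that PFS loses power under the plan or is undersized. The documents do not support that. The 407 events deliver 90% at 0.005 with nothing recycled, so power is forgone, not lost. Nor is there a type I error fault, since unused alpha makes the procedure conservative.

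A reader might also take the largest gains, about 25 points at HR 0.75 and 30 at HR 0.80, as the expected benefit. They require PFS to weaken while every other effect stays at its design value, which pairs a PFS hazard ratio of 0.80 with an iPFS hazard ratio of 0.60. If all effects shrink together, the gains fall to roughly 10 to 13 and 8 to 10 points.

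Finally, the return cannot rescue the trial. It needs OS to have been rejected already, so the chance of at least one primary success is the same either way. The PFS estimate and 95% confidence interval are reported regardless. All of this limits the value of the change, but none of it supplies a reason to exclude PFS.

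**Conclusion.** The point holds as a free improvement. When the other four tested hypotheses are rejected and PFS has 0.005 < p <= 0.05, the plan leaves 0.045 unused, although returning it would take nothing from any other hypothesis and would keep familywise error within 0.05. The forgone PFS power is about 5 to 7 points at the design effects (8.3 at most). At weaker PFS effects it depends on how the other effects move.

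These sizes rest on assumed correlations, on one-time testing (OS in fact has four analyses), and on edges inferred from SAP Table 5. The 407-event reproduction, the critical hazard ratios and the unused 0.045 do not depend on the correlations.

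**What to change.** - In Protocol Figure 3 and SAP Figure 1, give H5 (OS subgroup) an edge of weight epsilon to H2 (PFS) and 1 − epsilon to H1 (OS), with epsilon vanishingly small.
- In Protocol 10.4.1.4 and SAP 8.1.4, delete the item 1 sentence that bars alpha from returning to H2 and the item 3 clause that excepts PFS from re-testing. Delete the matching note in SAP Appendix B.
- State that once H1, H3, H4 and H5 are all rejected, PFS is re-tested on its frozen 407-event primary-analysis data at two-sided 0.05, or at the matching group-sequential level if a PFS interim was held. SAP Appendix B expects the PFS primary analysis to come first, so the interim case is a contingency.
- Add the row to SAP Table 5 and the case to SAP Figure 5.

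The cost is one edge and a few sentences, to be settled before any efficacy result is seen; Amendment 5 records that it preceded any formal efficacy evaluation of PFS or OS. No patients, looks or data are added, and no alpha is taken from another hypothesis. The limit is timing: a PFS claim made this way may come later than the PFS primary analysis (month 48 in Protocol Table 12), because it waits for the other four rejections. If the sponsor prefers to keep the exclusion, the SAP should give the reason.

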1. OBJECTIVES

1.1 Primary

The primary objectives are:

Primary Objectives:

Phase 1b:

- To evaluate the safety, as assessed by incidence of dose limiting toxicity (DLT), of talimogene laherparepvec in combination with pembrolizumab in subjects with previously untreated, unresectable, stage IIIB to IVM1c melanoma.

Phase 3:

- To evaluate the efficacy of talimogene laherparepvec with pembrolizumab versus placebo with pembrolizumab, as assessed by progression-free survival (PFS) (response evaluation by blinded independent central review using modified Response Evaluation Criteria in Solid Tumors [RECIST] 1.1) and overall survival (OS).

1.2 Secondary

The secondary objectives are:

Phase 1b:

- To evaluate the efficacy of talimogene laherparepvec in combination with pembrolizumab as assessed by:
 - Confirmed objective response rate (ORR), best overall response (BOR), durable response rate (DRR), duration of response (DOR), disease control rate (DCR), and PFS (response evaluation by investigator using modified immune-related Response Criteria [irRC])
 - OS
- To evaluate the safety of talimogene laherparepvec in combination with pembrolizumab as assessed by incidence of treatment-emergent and treatment-related adverse events, and abnormal laboratory tests.

Phase 3:

- To evaluate the efficacy of talimogene laherparepvec with pembrolizumab versus placebo with pembrolizumab, as assessed by:
 - Complete response rate (iCRR) by blinded independent central assessed modified immune-related response criteria simulating response evaluation criteria in solid tumors (modified irRC-RECIST)
 - iPFS by blinded independent central assessed modified irRC-RECIST
 - OS in subjects excluding stage IVM1c per case report form (CRF)
 - ORR, BOR, DRR, DOR, and DCR (response evaluation by blinded independent central review assessed using modified RECIST 1.1), and iORR, iBOR, iDRR, iDOR, and iDCR by blinded independent central review assessed using modified irRC-RECIST)

[figure not shown]
- To evaluate the safety of talimogene laherparepvec with pembrolizumab versus placebo with pembrolizumab, as assessed by incidence of treatment-emergent and treatment-related adverse events, and abnormal laboratory tests.
- To evaluate patient reported outcomes (PRO) in phase 3 as assessed by the European Organization for Research and Treatment of Cancer (EORTC) Quality of Life Questionnaire Core 30 (QLQ-C30) Global Health Status/Quality of Life (GHS/QoL) subscale.

1.3 Exploratory

The exploratory objectives are:

[figure not shown]
Phase 1b:

- To evaluate whether talimogene laherparepvec induces changes in PD-L1 expression by immunohistochemistry (eg, negative to positive) in injected and non-injected lesions after starting talimogene laherparepvec in subjects whose tumors are PD-L1-negative prior to receiving talimogene laherparepvec in phase 1b.

[figure not shown]

Phase 3:

- iORR, iBOR, iDRR, iDOR, iDCR, and iPFS (response evaluation by investigator-assessed modified irRC-RECIST).

- To evaluate the incidence of anti-pembrolizumab antibodies when pembrolizumab is administered in combination with talimogene laherparepvec or placebo.
- To evaluate the pharmacokinetics (PK) of pembrolizumab when administered in combination with talimogene laherparepvec or placebo.
- To evaluate PROs as assessed by the EORTC QLQ-C30 subscales.
- To estimate health state utility (HSU) values using the EuroQoL-5D-3 Level (EQ-5D-3L).

Approved

